#### 4.650 FOLLOW-UP VISIT REQUIREMENTS

All subjects are required to have a follow-up visit at 30 days, 6 months, and 1 year postprocedure. Tables 4-6 below list the follow-up assessment requirements and visit windows, according to number days following the index procedure.

Table 4: 30-Day Follow-Up	Visit Requirements
---------------------------	--------------------

Follow-up Requirements	Target	Window
Rutherford Clinical Category assessment		
Ankle-brachial index		
WIQ	30 Days	30-45 Days
Duplex Ultrasound*		
Adverse event evaluation		
* First duplex ultrasound can occur any time within 45 days of the procedure. Must be conducted		

\* First duplex ultrasound can occur any time within 45 days of the procedure. Must be conducted per Duplex Ultrasound Protocol. Copies must be sent to the Ultrasound Core Laboratory for review.

#### Table 5: 6-Month Follow-Up Visit Requirements

Follow-up Requirements	Target	Window
Rutherford Clinical Category assessment	180 Days	150-210 Days
Ankle-brachial index		
WIQ		
Duplex Ultrasound*		
Adverse event evaluation		
*Must be conducted per Duplex Ultrasound Protocol. Copies must be sent to the Duplex Ultrasound Core Laboratory for review.		

### Table 6: 1-Year Follow-up Visit Requirements

Follow-up Requirements	Target	Window
Hemoglobin A1C	365 Days	320-410 Days
Creatinine		
Rutherford Clinical Category assessment		
Ankle-brachial index		
WIQ		
Duplex Ultrasound*		
Adverse event evaluation		
*Must be conducted per the Core Laboratory Protocols. Copies must be sent to the Core Laboratories for review.		

#### 4.651 UNSCHEDULED AND RE-INTERVENTION VISITS DURING FOLLOW-UP

Completion of study assessments at unscheduled follow-up visits prior to the 1-year visit should be done as clinically indicated and corresponding data should be documented and submitted to the Sponsor.

If a subject is clinically indicated for a re-intervention of the target lesion prior to the 1year follow-up visit and the subject does not want to proceed with an invasive angiogram or re-intervention, it will not be considered a deviation from the Study Protocol. If possible, all non-invasive assessments should be captured for the study, including ABI, RCC, WIQ, and duplex ultrasound, even if the re-intervention and angiogram are declined. Copies of any angiographic or duplex ultrasound results must be sent to the appropriate core laboratory. These data will be collected and used for adjudication by the Clinical Event Committee for "clinically-driven" reintervention.

The investigator will initially determine the lesion severity by visual estimate prior to re-intervention. The cine angiogram will be sent to angiographic core lab for analysis. Two orthogonal views of the lesion will be required to determine more accurately the lesion severity by the core lab. Core lab evaluation of lesion severity will be used as the more definitive measure and supersedes operator's visual estimate.

The following describes what take precedence (angiogram versus duplex ultrasound) to determine lesion severity:1. Patient has both modalities because of symptoms recurrence prior to 6 months follow up. To be consistent with the 6 months' primary endpoint the Duplex ultrasound will take precedence

2. Patient has angiogram only because of symptom recurrence prior to 6 months. In this case the angiographic finding of loss of patency will be used as no Duplex ultrasound was performed. The Duplex ultrasound at 6 months post reintervention will not be used even if performed as it is post re-intervention.

3. Patient undergoes both modalities at 6 months because of symptoms. Duplex ultrasound will take precedence as long as it has been done prior to the angiogram and re-intervention.

#### 4.652 TERMINATION OF PARTICIPATION

All subjects have the right to withdraw from participation at any point during the study. In addition, Principal Investigators also have the ability to terminate subject participation in the study. A description of the reason for a subject's termination will be documented. Reasons for termination include: subject withdrawal, physician-directed subject withdrawal, and lost-to-follow-up.

#### 4.653 LOST TO FOLLOW-UP

Every attempt must be made to have all subjects complete the required follow-up visits according to the visit schedule. A subject will not be considered lost-to-follow-up unless efforts to obtain compliance are unsuccessful. At a minimum, the effort to obtain follow-up information must include three attempts to make contact via telephone. Telephone contact efforts to obtain follow-up must be documented in both the subject's medical records and on the study electronic case report forms (eCRFs).

#### 4.654 SUBJECT WITHDRAWAL

Whenever possible, the site staff should obtain written documentation from the subject that wishes to withdraw his/her consent for future follow-up visits and contact. If the site staff is unable to obtain written documentation, all information regarding the subject's withdrawal must be recorded in the subject's medical record. In addition, the appropriate eCRFs must be completed for the subject and clear documentation of the subject's withdrawal must be provided to the Sponsor.

Withdrawal of a subject from the study can occur at the discretion of the Principal Investigator or the Sponsor. Reasons for physician and/or Sponsor-directed subject withdrawal include, but are not limited to: the subject is not adhering to the Study Protocol requirements, the subject has enrolled in another study that conflicts with this Study Protocol outcomes, or if it is in the best interest for the safety or welfare of the subject to withdraw.

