### 5.2 DATA ANALYSIS PLAN

#### **5.23** GENERAL PRINCIPLES

All statistical analyses will be performed using a widely accepted statistical or graphical software. An intention to treat analysis will be carried on with bailout stenting as TLR and without bail out stenting as TLR. Also analysis will be done by actual treatment. A maximum of 140 patients will be enrolled.

Descriptive statistics will be used to present the data and to summarize the results. Discrete variables will be presented using frequency distributions and cross tabulations. Continuous variables will be summarized by presenting the number of observations (N), mean, standard deviation, median, minimum, and maximum values.

For AE reporting, the primary analysis will be based on subject counts. A subject with more than one event will be counted only once toward the event rate based on the total number of subjects with AEs. An event rate based on event counts will also be presented. For example, if a subject experiences one major unplanned amputation of the treated limb and two clinically-driven TLRs within 30 days, the subject will be counted once in the rate of total subjects with a 30-day MAE; the same subject will be counted once in the individual event category of "Major Unplanned Amputation of the Treated Limb" and twice in the "Clinically-Driven TLR" category.

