### **11.0 PUBLICATION STRATEGY**

At the conclusion of all 1-year follow-up visits, a multi-site abstract reporting the preliminary results may be prepared and presented at one or more major endovascular meetings by [name]. A multi-site publication may also be prepared for print in a peer-reviewed scientific journal at the conclusion of the study. Following the national PIs ([name] and [name]), additional co-authors will be added to the main manuscript by order of number of patients enrolled in the study. Final number of coauthors will be determined based on patient enrolment, quality of data and lack of significant protocol violation. Investigators with significant protocol deviations that jeopardize data quality may not be considered as authors. The final decision for co-authorship will be determined by the Sponsor.

The publication of results from any single-site experience within the study must not be submitted for publication (by itself or as part of other registries) until approval from the Sponsor is granted and after the publication of the main manuscript. A proposal for a publication will be sent to the Sponsor for review and approval. MCRF will review and approve all publications for presentation at any meeting or for publications in journals or magazines. A significant contribution by each author is expected for authorship. The national PIs are expected to review, approve and co-author any additional publications prior to submission to Journals or other publications media resulting from this study.

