#### **Patency Classifications:**

- Patency via Duplex (Peak Systolic Velocity ≤ 2.5): Defined by duplex ultrasound measurement of peak systolic velocity (PSV) ratio ≤ 2.5 at the target lesion.
- **Patency via angiography:** Defined as < 50% stenosis per angiography as determined by the Angiographic Core Laboratory.
- Assisted primary Patency: Defined as < 50% stenosis per angiography or duplex as maintained by repeat percutaneous intervention of a non-occluded vessel
- Secondary Patency: Defined as < 50% stenosis per angiography or duplex, as maintained by repeat percutaneous intervention of a non-occluded or occluded vessel

**Percent Stenosis:** Native vessel diameter as measured at the most narrow point of the lesion divided by the estimated native vessel diameter (the mean of the vessel diameters proximal and distal to the lesion) at that location.

% Stenosis =  $\frac{Diameter \ at \ most \ narrow \ segment \ of \ lesion \ (mm)}{\left[\left(proximal \ vessel \ diameter \ + \ distal \ vessel \ diameter \right)/2\right]}$ 

**Physician-Directed Subject Withdrawal:** Withdrawal of a subject from the study at the direction of the Principal Investigator. Reasons for physician-directed subject withdrawal include, but are not exclusive to: the subject is not adhering to the Study Protocol requirements, the subject has enrolled in another study that conflicts with the JET-ISR outcomes of interest, or the physician deems it in the best interest for the safety or welfare of the subject to withdraw.

Pre-Procedure: The time until the procedure begins (before arterial access is obtained).

**Principal Investigator:** Physician responsible for overall clinical management of subjects enrolled at his/her institution. Assumes overall responsibility and accountability for the clinical team and for data obtained from each subject participating in the study. Ensures compliance with the Study Protocol, applicable laws, and applicable regulations; ensures informed consents are signed, and reviews and signs eCRF indicating documents are accurate and complete.

**Procedural Outcome:** Categorized by < 30% residual stenosis following the protocol-defined treatment (JS + PTA) with provisional or bail out procedures as determined by the Angiographic Core Laboratory.

**Procedural Success:** Defined as  $\leq$ 30% residual diameter stenosis following JS + PTA without provisional or bailout procedures.

Protocol Deviation: Any divergence from the Study Protocol.

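### Investigator- or sponsor-directed withdrawal is not separated from outcome follow-up, and the ITT handling of withdrawn patients is undefined, so later TLRs can be lost selectively

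*Combined protocol and SAP*

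**What the plan says.** Section 4.654 states: "Withdrawal of a subject from the study can occur at the discretion of the Principal Investigator or the Sponsor". The reasons are introduced by "Reasons for physician and/or Sponsor-directed subject withdrawal include, but are not limited to", and the first two named are "the subject is not adhering to the Study Protocol requirements, the subject has enrolled in another study that conflicts with this Study Protocol outcomes"; the third is the subject's safety or welfare. Section 12.0, under Physician-Directed Subject Withdrawal, gives the investigator the same power ("Withdrawal of a subject from the study at the direction of the Principal Investigator") and again names non-adherence and the case where "the subject has enrolled in another study that conflicts with the JET-ISR outcomes of interest".

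At withdrawal, Sections 4.652 and 4.654 ask for the reason, the relevant case report forms and documentation of the withdrawal. Neither asks for later outcomes. Section 4.653 covers a different group, patients who cannot be reached: "At a minimum, the effort to obtain follow-up information must include three attempts to make contact via telephone".

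On analysis, Section 5.23 says: "An intention to treat analysis will be carried on with bailout stenting as TLR and without bail out stenting as TLR". Sections 4.2 and 5.25 also label the primary TLR comparison intention to treat. Section 5 does not define the ITT denominator, a censoring rule, an imputation or a sensitivity analysis. Missing outcomes are addressed only by enrolling extra patients for a 20% loss (5.12, 5.25). Section 4.47 says blinding is not possible.

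**The concern.** JetStream treatment is a single index procedure. Failing to follow protocol requirements afterwards is no reason to stop recording whether the lesion was re-treated or the patient died. The conflicting-study reason is more awkward. A patient whose stent narrows again and who enters another restenosis study to have that lesion re-treated is having the primary event as Section 4.2 defines it. Section 4.654 allows that patient to be withdrawn at or before the event.

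The decision can be made with symptoms and duplex results in view. No concurrent arm has the same losses, because the comparator is a fixed published count. If withdrawal is related to impending TLR and the later outcome is not sought, the observed JetStream rate is biased downward against 69/182. The independent Clinical Events Committee (4.664) and core laboratories (4.662, 4.663) can classify only the events that reach them.

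**Working it through.** **Inputs.** Historical control 69/182 = 37.9% (Appendix A). Planning rates 0.38 and 0.21, power 0.80, type I error 0.05, uncorrected chi-squared, 20% loss (5.12). Maximum enrolment 140 (5.25). Feasibility events: 2 bailout stents and 4 later TLRs in 29 limbs (Appendix A).

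**Step 1: the plan's sample size.** With p̄ = (0.38 + 0.21)/2 = 0.295,

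n = [1.96·√(2·0.295·0.705) + 0.842·√(0.38·0.62 + 0.21·0.79)]² / 0.17² = 111.8, so 112 per group. This matches the plan when the 0.05 is two-sided.

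Allowing for loss, 112/0.80 = 140, the stated maximum. At 140 enrolled, the plan tolerates 140 − 112 = 28 patients without a 6-month outcome.

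**Step 2: which events are exposed.** Bailout stents count as TLR on the day of the procedure, and TLRs before withdrawal are already recorded. Only later TLRs can be lost. In the feasibility data these were 4 of 6 counted events.

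**Step 3: effect of losing k TLR-bound patients.** Assume, because the plan does not say, that a withdrawn patient leaves both numerator and denominator. For x/n against 69/182,

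χ² = (n + 182)·[x·113 − (n − x)·69]² / [n·182·(x + 69)·(n − x + 113)].

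- 41/140: χ² = 322·2198²/(140·182·110·212) = 2.618, p = 0.106.
- 37/136: χ² = 318·2650²/(136·182·106·212) = 4.015, p = 0.045.

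| Full result | p | k lost | Observed | p |
|---|---|---|---|---|
| 29/140 (20.7%, planned) | 0.0009 | not needed | already significant | – |
| 40/140 (28.6%) | 0.079 | 3 | 37/137 (27.0%) | 0.041 |
| 41/140 (29.3%) | 0.106 | 4 | 37/136 (27.2%) | 0.045 |
| 42/140 (30.0%) | 0.139 | 4 | 38/136 (27.9%) | 0.063 |
| 53/140 (37.9%, no benefit) | 0.99 | 4 | 49/136 (36.0%) | 0.73 |
| 53/140 (37.9%, no benefit) | 0.99 | 21 | 32/119 (26.9%) | 0.048 |

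Since 38/140 is already significant (p = 0.042), four or fewer losses reverse the test only for 39, 40 or 41 events in 140 (39/140, p = 0.058, becomes 38/139, p = 0.046, with one loss).

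**Step 4: false-positive rate.** In a simulation of 40,000 trials with a true rate of 0.379 in both groups and 140 enrolled, the chance of a significant result favouring JetStream was about 2.4% with no selective loss. It was 6.6%, 15% and 30% when 10%, 20% and 30% of TLR patients were lost. These fractions are assumptions and apply to all TLRs. If only 4/6 of events are exposed, losing 10% of all means losing 0.10/(4/6) = 15% of the exposed ones.

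**Step 5: what a sensitivity analysis would show.** Suppose 24/112 (21.4%, p = 0.003) is observed with 28 of 140 missing. If 14 of the 28 had a TLR, the result is 38/140 (p = 0.042); if 15 had, 39/140 (p = 0.058); if all had, 52/140 (37.1%, p = 0.89).

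**The case against.** The documents are silent on post-withdrawal data; they do not forbid collecting it. Partial safeguards exist. Data from unscheduled visits must be submitted, and non-invasive assessments are captured if possible when re-intervention is declined (4.651). Serious adverse events are reported within 24 hours (4.657), the events committee reviews all reported events (4.664), and Section 4.653 asks for every attempt, with three calls only as a minimum. The consent form was not available for review and may already allow record access. All of this stands. It narrows the gap, but none of it requires TLR status at 6 months after a directed withdrawal.

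A reader might infer more than the documents support:

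- **That the rule contradicts ITT.** No section says withdrawn patients leave the ITT set. The denominator is undefined, which is a different fault.
- **That the lost data could never be recovered.** Repeat procedures and deaths may be in medical records, and Section 9.6 lets sponsor staff review them. For withdrawn patients, recovery depends on consent.
- **That non-adherence can only mean missed visits.** Section 4.647 also sets post-procedure antiplatelet requirements.
- **That authorship rules motivate withdrawal.** Section 11.0 says "Investigators with significant protocol deviations that jeopardize data quality may not be considered as authors". That concerns serious deviations, and withdrawing a patient does not erase one already recorded. Nothing shows such conduct or intent.

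**Conclusion.** The point holds as a gap in outcome ascertainment and analysis rules. A discretionary, open-ended withdrawal power, no required TLR or vital status afterwards, no blinding and a fixed historical comparator together allow later primary events to be lost selectively.

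Its size depends on two things the documents do not give: how many patients would be withdrawn this way, and whether they leave the denominator. Assuming they do, 3 to 4 TLR-bound losses reverse the conclusion only near 29%. It would be wrong to infer that a handful of withdrawals could manufacture a positive trial: at the planned 21% the result is significant without them, and with no benefit about 21 selective losses would be needed. Twenty-one is within the 28 losses the plan tolerates, but comparing the two says nothing about likelihood, since the 28 cover loss for any reason.

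**What to change.** - **Section 4.654 and the Section 12.0 definition:** state that investigator- or sponsor-directed withdrawal, for any reason, ends study visits only and not outcome follow-up, and that non-adherence or joining another study is not a reason to stop outcome follow-up. Deleting those two reasons would not suffice, because the list is open-ended.
- **Data collection:** only the patient's own withdrawal of consent ends it, with TLR and vital status then taken from site records where the consent allows.
- **Primary endpoint:** confirm that re-treatment of the index lesion within another study counts as a TLR. The current definition already implies this.
- **Section 4.653:** require a site-record check for repeat procedures and death before a patient is classed as lost.
- **Section 5:** define the ITT set as all enrolled patients, and add a tipping-point or worst-case analysis for those still without a 6-month outcome.

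The cost is protocol wording, chart checks for a few patients and possibly one sentence in the consent form. The JetStream rate may come out slightly less favourable.

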#### 4.655 DEVIATIONS TO THE STUDY

Principal Investigators and site staffs should avoid Study Protocol deviations. Any deviations from clinical protocol requirements will be considered protocol deviations and need to be reported to the Sponsor. Any emergency deviations (deviations from the Study Protocol to protect the life or physical well being of a subject, such as, surgical repair of the target vessel) that occur must be reported to the Sponsor and the site Ethics Committee (EC) per their local guidelines.

#### 4.656 Adverse Events

#### 4.657 ADVERSE EVENT DEFINITIONS

Serious Adverse Event (SAE) is defined as any untoward and unintended clinical sign, symptom, or disease in a subject, regardless of the relationship between the adverse event and the device under investigation, that:

- Led to a death,
- Led to a serious deterioration in the health of the subject that:
  - 1. Resulted in a life-threatening illness or injury,
  - 2. Resulted in a permanent impairment of a body structure or a body function,
  - 3. Required inpatient hospitalization or prolongation of existing hospitalization, or
  - 4. Resulted in medical or surgical intervention to prevent permanent impairment to a body structure or body function.
- Led to fetal distress, fetal death or a congenital abnormality or birth defect.

A written report must be provided to the Sponsor or representative within 24 hours of the Investigator learning of an SAE and must be provided to the EC according to reporting guidelines.

### 4.658 Adverse Event Classifications

In addition to the definitions above, adverse events will be classified as follows:

#### Major Adverse Events

- 1. Major Adverse Events (MAE) as individual endpoints in-hospital and up to 30 days : Include device-induced vascular injury as reported by the operator, amputation (major and minor unplanned), death, significant distal embolization requiring the use of pharmacologic or mechanical means to treat (other than a vasodilator), perforation (extravasation of blood outside the vessel wall), major bleeding, non-fatal myocardial infarction (defined as the occurrence of more than 20 minutes of chest pain post procedure with an increase in troponin), stroke, access complications (AV fistula and pseudoaneurysm), bail out stenting, acute renal failure (drop in crcl by > 25% from baseline), acute ( $\leq$  24 hours) or subacute ( $\leq$  1 month, > than 24 hours) vessel closure.
- 2. Target Lesion failure at 6 months and 1 year: Defined as major unplanned amputation related of the treated limb, vascular mortality related to treated limb and target lesion revascularization at 6 months and 1 year (stenting in the lab is not considered a TLR)
- **3.** Major Adverse Event Rate at 6 months and 1 Year: Defined as major unplanned amputation of the treated limb, all-cause mortality or TLR at 6 months and 1 year (bail out stent in the Lab is included as TLR)

**Unanticipated or Unexpected Adverse Device Effects:** any serious adverse effect on health or safety or any life-threatening problem or death caused by, or associated with, a device, if that effect, problem, or death was not previously identified in nature, severity, or degree of incidence in the protocol or application (including a supplementary plan or application), or any other unanticipated serious problem associated with a device that relates to the rights, safety, or welfare of subjects.

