#### INTENDED USE

The JS device catheter is intended for use in peripheral arterial intervention to treat denovo and non-stent restenotic infrainguinal lesions. JS is not intended for use in the coronary, carotid, iliac or renal vasculature.

JS application in treating FP ISR is off label and considered investigational

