The recently presented final data of the JetStream ISR study at New Cardiovascular Horizon 2015 (one year TLR data will be presented at LINC 2016) evaluated acute procedural and 6-month outcomes, and stent-device interaction of the JetStream Navitus in treating FP ISR from 2 U.S. centers (manuscript in Print in JEVT 2016. Copy of accepted manuscript is in Appendix B). Demographic, clinical, angiographic and procedural data were collected on 29 patients (32 limbs) included. The primary effectiveness endpoint was acute procedural success (<30% residual narrowing with no serious adverse events). The primary safety endpoint was freedom from major adverse events (MAE). Secondary endpoints include clinically driven target lesion revascularization (TLR) at 6 months and stent integrity as assessed by Angiographic Core Laboratory. Six-month follow-up was completed on 27 patients (29 limbs). Adjunctive balloon angioplasty was performed in 100% at a mean pressure of  $11.6 \pm 3.3$  atm. Total lesion length was  $17.4 \pm 13.1$  cm and total treated length  $19.5 \pm 12.9$  cm. Acute procedural success occurred in 90.6% of limbs. Acute device success (<50% residual narrowing after atherectomy alone) was 75.9%. Embolic filter protection (EFP) was used in 16/32 (50.0%) of limbs. Macrodebris was noted in 2/16 (12.5%) of filters and distal embolization (DE) requiring treatment occurred in 3/32 limbs (9.4%) (2 with no EFP). There were no new stent fractures or deformities (n=24) post JS. On 6-month follow-up TLR occurred in 4/29 patients (13.8%). Patency rate (PSVR<2.4) was 72%. Other nonprocedure related adverse events were total death 3.4% and major bleeding 3.4%. These results were highly encouraging establishing in this feasibility small study the safety and effectiveness of the JetStream in treating FP ISR when compared to historic control.

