### Safety

**Major Adverse Events (MAE) at 30 days**: unplanned amputation, total mortality or TLR at 30 days (TLR includes bail out stenting)

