#### 4.62 ANGIOGRAM

A sheath will be inserted and after insertion the subject should receive anticoagulation medications as indicated by the Investigator to maintain appropriate clotting time. Selective angiography of the limb to be treated including the distal aorta, bilateral iliac, ipsilateral femoral, popliteal and tibial-peroneal vessels (to the pedal level) will be performed to identify the anatomical characteristics of the vasculature and to best isolate and define the lesion. If a pre-procedure assessment has been completed with CTA/MRA, the angiography can be limited to the target vessel, with a baseline assessment of run-off. Angiography must be conducted according the Angiographic Protocol (refer to Core Lab requirement). Gadolinium and CO2 are not allowed for use as contract material.

During angiography the Investigator performing the procedure will assess the subject for the angiographic inclusion and exclusion criteria. It is required that a radiopaque ruler be used to define lesion length and define anatomical measurement references. If the subject meets all the angiographic inclusion criteria and does not meet any of the angiographic exclusion criteria, the subject is enrolled when an exchangeable guidewire crosses the target lesion. Upon enrollment, subjects will be then treated with the JS + PTA as per protocol.

Angiographic films, including run-off, will be obtained immediately prior to and after treatment (after JS alone, and after adjunctive PTA or bail out stenting) according to the Angiographic Core Lab Protocol. Capture images that demonstrate the stenosis in two views that minimize the degree of vessel overlap and demonstrate the stenosis in its most severe view. Angiographic results must be sent to the Angiographic Core Laboratory.

The Angiographic Core Laboratory assessments will supersede the measurements by the Investigator performing the procedure for data analysis purposes; however, the measurements by the Investigator performing the procedure will be used to determine subject eligibility at the time of enrollment.

The Angiographic core laboratory will also assess stent fracture location and severity at baseline prior to any treatment and post atherectomy to assess for additional/worsening fractures.

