#### 4.664 CLINICAL EVENTS COMMITTEE

An independent Clinical Events Committee (CEC) will be established. The CEC will consist of physicians who are not Investigators in the study and who do not have any significant investment in Boston Scientific, Bard or any of their entities. The committee may include, but not be limited to, the specialties of interventional cardiology, vascular surgery, and interventional radiology.

The CEC is responsible for reviewing all reported adverse events. The CEC will classify the pertinent outcome events as defined in the Study Protocol.

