#### 6.2 POTENTIAL RISKS

#### 6.3 **RISKS ASSOCIATED WITH PLAQUE EXCISION**

The risks associated with JS atherectomy of the SFA and/or popliteal artery may include, but are not limited to, the following:

- Access site complications
- Amputation
- Arterial dissection
- Arterial perforation
- Arterial rupture
- Arterial spasm
- Arterial thrombosis
- Arterio-venous (AV) fistula
- Bleeding complications
- Death
- Embolism
- Device getting stuck on stent
- Wire breaking during atherectomy
- Emergency or non-emergency arterial bypass surgery
- Hypotension
- Infection
- Ischemia
- Restenosis of the treated segment
- Total occlusion of the peripheral artery
- Vascular complications which may require surgical repair
- Disruption of previously implanted stent

As with any device requiring mechanical deployment and retraction, there exists a risk of mechanical failure of the device resulting in potential surgical intervention.

All of the above could cause prolonged illness, permanent impairment of daily function or, in rare cases, death. Possible treatments could include, but are not limited to, vascular surgery.

Extensive reliability engineering testing has been performed on the study device to mitigate risks to the subject due to product failure. Additionally, studies using the JS device have been conducted to ensure that the systems perform as intended without introducing more risks during the index procedure or during follow-up. Risks of atherectomy may be further limited by providing medications such as aspirin or clopidogrel and continuing to monitor subjects following treatment.

While some of the potential risks identified have occurred in prior atherectomy trials, and while Boston Scientific believes that the risk for significant injury or death due to the JS XC device is quite low, these risks have yet to be adequately and fully quantified. These risks in applying the JS to in-stent restenosis has not been defined in a large trial but early preclinical data and the JetStream ISR feasibility study has shown that the device performed safely with no devicestent interaction.

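### Device-induced vascular injury is counted on operator report alone, and the core-lab stent-fracture reading is tied to no outcome

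*Combined protocol and SAP*

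**What the plan says.** **Vascular injury.** The list of individual in-hospital and 30-day major adverse events (MAEs) appears in the Synopsis (secondary endpoint 10), section 4.658 and section 12.0. In all three places its first item reads "Include device-induced vascular injury as reported by the operator". Under section 4.664, "The CEC is responsible for reviewing all reported adverse events".

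**Stent fracture.** Section 4.62 says the core laboratory "will also assess stent fracture location and severity at baseline prior to any treatment and post atherectomy to assess for additional/worsening fractures". Section 6.3 lists "Disruption of previously implanted stent" among the risks of the procedure and says that the risks of JS in in-stent restenosis have not been defined in a large trial. On the feasibility study, section 3.32 states: "Secondary endpoints include clinically driven target lesion revascularization (TLR) at 6 months and stent integrity as assessed by Angiographic Core Laboratory". It reports no new fractures or deformities (n=24).

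**Setting.** According to the Intended Use section, "JS application in treating FP ISR is off label and considered investigational". The trial is single-arm and unblinded (sections 4.1 and 4.47). The primary safety composite in section 4.2 is "unplanned amputation, total mortality or TLR at 30 days (TLR includes bail out stenting"), so it contains neither item.

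**The concern.** In a single-arm trial the safety message is a set of absolute event rates, so who finds the events matters as much as how they are defined. For vascular injury the plan names one source, the person who did the procedure, while an independent laboratory holds the films on which an injury could be seen. If that source misses or omits events, the reported rate is too low, and there is no concurrent control arm to show it.

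Fracture has the opposite problem. The reading is independent and done before and after atherectomy, but nothing says where the result goes. It concerns a harm particular to cutting inside a stent. Section 3.1 also associates significant stent fractures with a higher rate of restenosis. Only Class III and IV fractures are excluded (section 4.4.2, item 19), so lower-class fractures can enter and could worsen.

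**Working it through.** The plan gives no figure on this point to reproduce. The check is a tracing exercise, followed by a short calculation for context.

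**1. Can an injury the operator does not report reach the MAE count?**

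- *Definition.* All three lists name the operator as the source. No other item in the list carries a source qualifier.
- *Clinical Events Committee (CEC).* Section 4.664 limits it to reported events. Section 6.4 has it adjudicate every adverse event, but creates no route for one that nobody reports.
- *Core-lab precedence.* In section 4.62 core-lab assessments override the investigator's measurements. That covers quantities such as percent stenosis; it does not assign the core lab to detect injury.
- *Core-lab review of bail-out stenting (section 4.644).* This reaches only patients who were stented.
- *Films.* Section 4.62 requires images before treatment, after JS alone, and after adjunctive PTA or stenting. Section 4.662 has the core lab review all angiographic procedure data.

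Dissection is the practical case. Section 6.3 lists it as a risk and section 12.0 gives the NHLBI grades A to F, but it is not an MAE item of its own. Unless it leads to a bail-out stent, closure or another listed event, its only way into the count is the operator-reported item.

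**2. Where does the fracture reading go?**

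| Place | New or worsened fracture named? |
|---|---|
| Primary outcomes (4.2) | No |
| Secondary outcomes (4.3, items 1–15; Synopsis, items 1–16) | No |
| MAE lists (4.658; 12.0) | No |
| Stopping rule (Synopsis, DSMB) | No |
| Analysis sections 5.23 to 5.26 | No |

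General adverse-event reporting may not catch it. Section 12.0 defines an adverse event as a clinical sign, symptom or disease, which a silent radiographic fracture may not meet. The unanticipated-effect category covers effects not previously identified in the protocol, and stent disruption is already identified there.

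**3. What the fracture reading could show**

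For zero events in n, the one-sided 95% upper bound is 1 − 0.05^(1/n). Inputs: n = 24 from section 3.32; n = 112 from section 5.12; n = 140 from section 5.23. The feasibility study treated 32 limbs and reported fracture on n = 24. If those 24 are limbs, 24/32 = 75% were evaluable. Carrying that share over is an assumption: 0.75 × 112 = 84 and 0.75 × 140 = 105.

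| n | Upper bound if 0 events |
|---|---|
| 24 (feasibility) | 11.7% |
| 84 (75% of 112) | 3.5% |
| 105 (75% of 140) | 2.8% |
| 112 | 2.6% |
| 140 | 2.1% |

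The documents give no expected fracture rate. At assumed true rates of 1%, 2% and 5%, the chance of at least one new fracture in 112 evaluable patients, 1 − (1 − p)^112, is 68%, 90% and 99.7%. Unless the true rate is very low, the core lab will probably see a finding for which the plan names no outcome.

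**The case against.** A reader might infer that the device's specific harms as a whole are self-reported or go unreported. The documents do not support that. Perforation, treated distal embolization, acute and subacute closure and bail-out stenting are separate items in the same list, without the operator qualifier. An unreported perforation is therefore the wrong example. Flow-limiting dissection of type D or higher may end in bail-out stenting, which the core lab reviews and which counts in both primary outcomes. Adverse events are evaluated during and at the end of the procedure, before discharge and at every visit (sections 4.59 and 4.646), and section 6.4 has the DSMB analyze procedural events. What remains is mainly lesser injury that needed no stent.

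Nor is fracture ignored: the before-and-after reading is prespecified and independent, and the descriptive analysis of procedural variables in section 5.24 could include it. The supportable statement is that it is collected but not named as an outcome. The core lab's Angiographic Protocol is not among the documents and may record dissection; even so, the MAE definition would still name the operator.

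Two further points stand. The lower fracture bound comes from film readings the plan already requires, so it measures what those readings are worth, not an effect of changing the wording. And calling every radiographic fracture a major adverse event would mix an imaging finding into a mostly clinical list.

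**Conclusion.** The point holds in this limited form. Device-induced vascular injury, as an individual 30-day MAE, depends on operator report, with CEC review of reported events only. Core-lab findings of new or worsened stent fracture are gathered without an outcome or a named analysis. The primary safety composite and the primary effectiveness test use neither item and are unaffected.

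Under-reporting of injury cannot be sized from the documents. A downward bias is plausible with a single unblinded source, but it is not demonstrated. For fracture, current evidence is compatible with a rate of up to 11.7%. Zero events in this trial would bring the bound to 2.1–2.6% if every patient has evaluable paired films, or 2.8–3.5% if 75% do. This is an inexpensive improvement to safety ascertainment and reporting, not a flaw in the trial's main conclusion.

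**What to change.** 1. In Synopsis endpoint 10, section 4.658 and section 12.0, replace the operator qualifier with: *as identified by the Angiographic Core Laboratory on the post-JS and final films (dissection by the NHLBI grades in section 12.0) or reported by the operator, CEC-adjudicated*. Device-induced vascular injury has no entry of its own in section 12.0, so the grades are needed to tell the core lab what to record.
2. Add to section 4.3 and the Synopsis a named secondary safety outcome: *new or worsened stent fracture after JS versus the pre-treatment film (core lab)*. Report it among patients with evaluable paired films, state that denominator, give an exact confidence interval, and supply it to the DSMB. Do not make it an MAE component.
3. In the same edit, reconcile the individual MAE list, which is a secondary endpoint in the Synopsis but is missing from section 4.3.

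The cost is protocol wording, one core-lab output field on films already read, and matching text in the core-lab and DSMB documents. No extra procedure is needed. The downside is a possibly higher reported injury rate.
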